6.6.4.2 Clinical chemistry

Albumin, alkaline phosphatase, total bilirubin, bicarbonate/CO₂, calcium, cholesterol, chloride, creatinine, CK, gamma-GT, glucose, HbA1c, LDH, inorganic phosphorus, lipase, amylase, magnesium, potassium, total protein, AST, ALT, sodium, triglycerides, BUN and uric acid will be measured. At timepoints on 6h, 24h, 48h and 72h samples have to be taken only for Mg, K, creatinine, Ca and glucose.

If the total bilirubin concentration is increased above 1.5 times the upper limit of normal, direct and indirect reacting bilirubin should be differentiated.

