1.4.2 Part 2 – Arms 2A-2B

Approximately 45 patients who meet the inclusion criteria will be randomized in a 2:1 fashion within 12 hours pre-transplant to receive one of the 2 treatment arms:

1. Arm 2A, n = 30: Basiliximab 20 mg (Days 0, 4) + CFZ533 at 10 mg/kg IV (17 doses) + MMF 1.0 g BID + CS
2. Arm 2B Control/SoC, n = 15: Basiliximab 20 mg (Days 0, 4) + Tac (4-11 ng/mL) + MMF 1.0 g BID + CS

Induction therapy must be started within 2 hours prior to transplantation, or according to local practice.

The first dose of CFZ533 will be administered IV pre-transplant or intra-operatively. Drug administration will begin after randomization and must be completed by the time of unclamping or up to 6 hours prior to the time of unclamping. Subsequent doses of CFZ533 will be administered IV (Arm 2A), over a period of 12 months.

Other study drugs must be started within 24 hours post-transplant. The second dose of basiliximab will be administered on Day 4, or according to local practice.

[figure not shown]
The day of randomization and transplant will be considered to be study Day 1.

Patients will then undergo Study Completion evaluations.

The primary endpoint of Part 2 will be assessed to determine whether the success criteria (safety and tBPAR) have been met when all patients have completed the Month 3 visit. If it is found that the data up to the Month 3 visit is inconclusive, a reevaluation (interim analysis) will occur after the Month 6 visit.

If the stopping rules are not met and the primary endpoint of Part 2 is fulfilled at Month 3, Part 3 (exposure-response profiling) will be initiated following consultation of the DMC. Cumulative efficacy and safety data will be collected on an ongoing basis during the conduct of the study.

Figure 1-2 Part 2 Design

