The following imputation method will be applied at each relevant timepoint for patients with missing eGFR values:

1. Patients that lose their graft before the timepoint in question will be assigned a value of zero for their missing eGFR value.
2. Patients that die or are lost to follow-up with a functioning graft before the timepoint in question will have an imputed value using the last-observation-carried-forward (LOCF) method.

Graft loss patients do not have a functioning graft, hence the lowest possible eGFR value (zero) will be assigned to such patients with missing eGFR values. In contrast, patients that die with a functioning graft, die for different reasons such as suicide, car accidents, cancer, therefore if they have a missing eGFR value, an imputed value using the LOCF method will be used. Similarly, patients who are lost to follow-up and have renal function, but are missing a Month 6 or Month 12 value for various reasons (e.g. moving from the area or not being able to make the site visit during the Month 6 or Month 12 visit) will have an imputed value using LOCF method for any missing eGFR value.

The mean eGFR results will be estimated from a longitudinal repeated measures mixed effects model using all the individual data collected until the timepoint of interest (1st IA Month 3 visit, 2nd IA Month 6 visit) whilst the patient is on treatment. From the model, estimates of the average at the timepoint of interest, treatment difference and 90% confidence

intervals will be obtained. The model will include fixed effects for treatment, time, donor age, donor type (living or deceased) and donor characteristic, treatment by time interaction and donor type by treatment by time interaction. An unstructured variance-covariance structure shall be used, however in the case that the model fails to converge, alternative structures would be tested. The estimates of the adjusted means and two-sided 90% CIs obtained from the model will be plotted over time.

The donor characteristic is a category that could have the result of “standard” or “expanded”.

Vital signs

All vital signs data will be listed by treatment, patient, and visit/time and if ranges are available abnormalities (and relevant orthostatic changes) will be flagged. Summary statistics will be provided by treatment and visit/time.

ECG evaluations

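### The eGFR model's donor type x treatment x time term leaves the single reported treatment difference without stated weights and exposed to an empty cell; donor type x time would serve better

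*SAP*

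**What the plan says.** SAP section 1.4.2 sets the size of Part 2: "Approximately 45 patients who meet the inclusion criteria will be randomized in a 2:1 fashion", with 30 patients on CFZ533 and, for control, "Arm 2B Control/SoC, n = 15". Protocol section 5.3 describes 2:1 randomization through IRT and states no stratification by donor type. Living and deceased heart-beating donors are both eligible (Protocol section 4.1), and no expected share is given.

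For eGFR, SAP section 7.1.2 fits one repeated-measures mixed model "using all the individual data collected until the timepoint of interest", naming the Month 3 and Month 6 interim analyses, and restricts it to data on assigned treatment. On the mean structure: "The model will include fixed effects for treatment, time, donor age, donor type (living or deceased) and donor characteristic, treatment by time interaction", and the list closes with the three-way term, in full "treatment by time interaction and donor type by treatment by time interaction". On the covariance: "An unstructured variance-covariance structure shall be used, however in the case that the model fails to converge, alternative structures would be tested". The required output is "estimates of the average at the timepoint of interest, treatment difference and 90% confidence" intervals. The section does not say how the treatment difference is averaged over donor type, or what happens if one donor type is absent from an arm.

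Protocol section 9.5.3.1 calls eGFR the key secondary and safety variable. Protocol section 9.7 takes 6.5 mL/min/1.73m² as the lower limit of clinically relevant benefit.

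**The concern.** The three-way term gives each arm a separate eGFR curve for living and for deceased donors. At Month 3 there are then two treatment effects, and the single reported difference has to be a weighted average of them. Because the weights are open, two programmers could report different differences and intervals from the same data.

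If the software default of equal weights is used, half the answer rests on the smaller donor group however few patients it holds. With 15 controls and no stated stratification, that group can be very small in the control arm. If it is empty at the visit of interest, the averaged difference cannot be estimated at all. The comparison at stake is the one meant to show the expected renal benefit of a CNI-free regimen.

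**Working it through.** **Inputs.** Arm sizes of 30 and 15 come from SAP 1.4.2. SDs of 16, 18 and 20 and the 6.5 threshold come from Protocol 9.7. Visits come from the Part 2 blood log (Protocol Appendix 1), because the Part 2 assessment schedule is not shown. The log has post-transplant laboratory samples at 6 h and Days 2, 3, 4, 15, 29, 57 and 85 (8 visits to Month 3), then Days 113, 141 and 169 (11 to Month 6). Protocol 6.6.4.2 confirms that the early samples include creatinine: "At timepoints on 6h, 24h, 48h and 72h samples have to be taken only for Mg, K, creatinine, Ca and glucose". The share of the smaller donor type is assumed, from 15% to 50%.

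**1. The plan's own precision figure.** Table 9-2 reproduces as d ± t(104) x SD x √(2/53). With SD 16 and d = 4.0 this gives (-0.01, 8.01) at 80% and (-2.16, 10.16) at 95%, against the printed (-0.0, 8.0) and (-2.2, 10.2). That table is for 53 per group. For 30 v 15 without covariates, the 90% half-width is t(43) x SD x √(1/30 + 1/15), which is 8.5 at SD 16 and 10.6 at SD 20. Both exceed 6.5 before the model is considered.

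**2. Widening from the three-way term at one visit.** Let a and b be the numbers with the smaller donor type in the CFZ533 and control arms, and take variances in units of SD².
- Variance of the effect in the smaller type: v1 = 1/a + 1/b. In the larger type: v2 = 1/(30-a) + 1/(15-b).
- With the term and equal weights: 0.25 x (v1 + v2).
- Without the term, donor type being adjusted for at that visit: 1/(1/v1 + 1/v2).

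Example at 20% (a = 6, b = 3): v1 = 0.500 and v2 = 1/24 + 1/12 = 0.125. With the term, 0.25 x 0.625 = 0.15625. Without it, 1/(2 + 8) = 0.100. The ratio of CI widths is √1.5625 = 1.25.

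Drawing a and b at random (binomial), over trials with no empty cell:

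| Smaller donor type | Median width ratio | 90th percentile |
|---|---|---|
| 20% | 1.28 | 1.74 |
| 30% | 1.10 | 1.32 |
| 40% | 1.03 | 1.12 |
| 50% | 1.01 | 1.05 |

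At 20%, three or fewer controls have the smaller donor type in 65% of trials. With observed-margin weights in the same formula, the median ratio is 1.00 throughout.

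**3. Empty cell.** At 20%, the control arm has none of the smaller type with probability 0.8^15 = 0.035, and the CFZ533 arm with 0.8^30 = 0.001. Together this is 3.6% (3.7% by simulation). With 21 v 11 patients left it is 9.4%. That second size borrows the 30% dropout of Table 9-2, which the documents do not state for Part 2.

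**4. Fit of the longitudinal model.** The SAP model was fitted by REML to simulated 30 v 15 trials, 300 per setting, with assumed trajectory, covariance and monotone loss. The comparator kept donor type as a constant main effect.
- Equal weights, median SE ratio: 1.02-1.05 at 50/50, 1.16-1.19 at 75/25 and 1.38-1.46 at 85/15.
- Observed-margin weights: 1.01-1.04.
- Month 3 with 30% loss, 90% half-width with v without the term: 10.7 v 10.3 (50/50), 12.4 v 10.3 (75/25) and 15.1 v 10.3 (85/15).
- Same settings, an empty cell at some visit: 0%, 6% and 21% of trials.

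**5. Parameter counts.** Covariance parameters are k(k+1)/2: 36 for 8 visits and 66 for 11. Mean parameters with the three-way term are 2 x 2 x 8 + 2 = 34 to Month 3. With donor type x time instead, they are 2 x 8 + 8 + 2 = 26. To Month 6 the counts are 46 and 35.

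**6. Convergence of the unstructured matrix.** At 8 visits every estimable fit converged. At 11 visits every fit converged with no loss, all but at most one per setting with 30% loss, and all but about 2-6% with 50% loss.

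**The case against.** The strongest reply is that the SAP does not prescribe equal weights. A reader might infer that the reported difference must be an equally weighted average, but the section is silent. With observed-margin weights almost all the widening disappears, and with a near-balanced donor mix little remains even under equal weights. This stands, and it makes the widening conditional on both a skewed mix and the default weights. It does not answer the empty cell, which breaks the estimate under either weighting.

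A reader might also infer that an unstructured covariance over many early visits is unworkable in 45 patients, so that the structure will probably be picked after seeing the fit. The checks do not support this. The matrix nearly always converged and did not itself widen the interval. Nor do the documents support counting 17 visits to Day 337 for this model: the section names Month 3 and Month 6 for it, although SAP 1.3.2 says renal function will also be assessed at Month 12. What remains is that the fallback structures are neither named nor ordered.

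It is also fair to say that most of the imprecision comes from 30 v 15, that the model sits under descriptive analyses, and that the proof-of-concept decision uses tBPAR alone (SAP 6.1.3). All of this is correct and limits the weight of the point.

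**Conclusion.** The point holds in a limited form. A single treatment difference is promised from a model in which the effect varies by donor type, with no weights and no empty-cell rule. Under equal weights the median CI is about 1.28 times as wide when the smaller donor type is 20% of patients and 1.10 times at 30%, and it is practically unchanged from 40% up. The chance of a non-estimable difference is about 4% at 20% with all 45 patients in the model, and it rises with a more skewed mix or loss from treatment. These sizes rest on an assumed donor mix, unstratified allocation and, for the longitudinal fits, an assumed covariance, trajectory and loss pattern.

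The documents do not support the stronger statement that the model will in general widen or break the comparison, or that the unstructured covariance is at fault. Even so, a model without the three-way term loses no material precision and removes the empty-cell failure, so the change is worth making.

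**What to change.** For the reported treatment difference and its 90% CI, replace donor type x treatment x time with donor type x time. Keep treatment x time, donor type, donor age and donor characteristic. Donor type x time needs to be written in, because the SAP lists no such term separately and the three-way term now carries it; without it the living-deceased gap would be forced constant over time. Present the effect by donor type in a separate descriptive table. Keep the visits before Day 15, since dropping them would discard prespecified on-treatment data.

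If the three-way term is kept, state that donor types are averaged with observed-margin weights and say what is reported when a donor-type-by-arm cell is empty.

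As a minor clarification, name the fallback covariance structures and their order.

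The cost is a change of SAP wording. The downside is that any difference in effect between living and deceased donors is then seen only descriptively.

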9.5.3.2 Other safety endpoints

Vital signs

All vital signs data will be listed by treatment, subject, and visit/time and if ranges are available, abnormalities (and relevant orthostatic changes) will be flagged. Summary statistics will be provided by treatment and visit/time.

ECG evaluations

All ECG data will be listed by treatment, subject and visit/time; abnormalities will be flagged. Summary statistics will be provided by treatment and visit/time.

Clinical laboratory evaluations

All laboratory data will be listed by treatment, subject, and visit/time and if normal ranges are available, abnormalities will be flagged. Summary statistics will be provided by treatment and visit/time.

Adverse events

All information obtained on AEs will be displayed by treatment and subject.

AEs and infections collected are to be coded with the MedDRA dictionary that gives preferred term and primary system organ class information. AEs and infection preferred terms are to be analyzed as a whole under the heading of AEs for each treatment arm. The incidence of AEs will be summarized by body system, severity and relationship to study drug by the following:

- AEs by primary SOC and PT
- AEs rated to have relationship to study drug by SOC and PT
- AEs by primary SOC, PT, and maximum severity
- SAEs by SOC and PT
- SAEs rated to have relationship to study drug by SOC and PT
- Deaths by SOC and PT
- AEs leading to discontinuation of a study drug by SOC and PT
- AEs leading to dose adjustment or interruptions of a study drug by SOC and PT
- infections by type of infection (viral, bacterial, fungal, and others) and microorganism of infection
- serious infections by type of infection and micro-organism of infection
- new onset diabetes mellitus (as defined in [Section 6.6.4.4](#))

- AEs by standardized MedDRA query (SMQ) levels (broad and narrow search)
- AEs by standardized MedDRA query (SMQ) and preferred term (broad and narrow search)

Multiple Occurrences for Tables:

In all tables about incidence rates of AEs / Infections, if a patient has multiple occurrences of an AE, this patient will be counted only once in the corresponding AE category. If a patient has multiple AEs within a system organ class, s/he will be counted only once for that class. If a patient has multiple severity ratings for an AE while on treatment, s/he is only counted under the maximum rating.

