Information pertaining to AEs noted during the study will be listed by patient, including the verbatim term given by the Investigator, the PT and SOC given by the MedDRA dictionary, start and end date, causality, severity, and relationship to study drug as assessed by the Investigator.

BK-polyoma viremia and nephropathy

The following variables will be analyzed descriptively:

- occurrence of BK-polyoma viremia any time post-transplantation “on treatment”
- occurrence of BK-polyoma viremia any time after switching a patient to SoC treatment
- occurrence of BK-polyoma virus nephropathy any time post-transplantation “on treatment”
- occurrence of BK-polyoma viremia any time after switching a patient to SoC treatment.

The difference of the investigational regimens to the control regimen will be summarized by risk ratios and appropriate CIs.

EBV, CMV and TB

All EBV, CMV and TB surveillance data will be listed by treatment, subject, and visit/time and if normal ranges are available, abnormalities will be flagged. Summary statistics will be provided by treatment and visit/time.

Laboratory data

Abnormalities according to clinically notable criteria will be identified. A by-subject listing of individual subject laboratory data will be generated. Values outside of the clinically notable limits will be flagged. Shift tables describing changes from randomization/enrollment based on the clinical notable criteria will be presented.

Descriptive statistics (mean, standard deviation, minimum, median and maximum) of quantitative laboratory variables, including change from randomization/enrollment, will be generated by visit.

New onset diabetes mellitus (NODAT)

The incidence of subjects developing new onset diabetes mellitus after transplantation (NODAT) will be summarized by treatment group. The probabilities of developing NODAT will be compared between treatment groups at 6 and 12 months post-transplant using logistic regression models with HbA1c levels at randomization/enrollment as predictive variables. Death, graft loss, or loss to follow up without NODAT before Month 12 will not be counted as developing NODAT. This analysis will be performed using subjects in the FAS population who do not have DM at randomization/enrollment.

Corporate Confidential Information

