All ECG data will be listed by treatment, patient and visit/time, abnormalities will be flagged. Summary statistics will be provided by treatment and visit/time.

Clinical laboratory evaluations

All laboratory data will be listed by treatment, patient, and visit/time and if normal ranges are available abnormalities will be flagged. A separate listing is provided presenting all parameters in a patient with any abnormal values. Summary statistics will be provided by treatment and visit/time.

Special clinical laboratory evaluations

Coagulation parameters prothrombin time and partial thromboplastin time will be listed by treatment, patient and visit/time. The coagulation parameters will also be presented graphically to show the overlaid patient profiles and mean profile over time for each parameter separately. Additionally overlaid patient profiles and mean profile over time will be presented graphically for platelets.

Cytokine assessments via multiplex cytokine including TNFa, IFNg, IL1b, IL2, IL4, IL8, IL10, IL12p, IL70 and IL13 will be listed by treatment, patient, and visit/time. The cytokine assessments will also be presented graphically to show the overlaid patient profiles and mean profile over time for each parameter separately.

Donor specific antibodies will be listed by patient and visit.

Immunogenicity data consisting of anti-CFZ533 antibodies information will be listed by patient and visit.

Virology monitoring results for hepatitis B, hepatitis C, HIV, Epstein-Barr Virus (EBV), cytomegalovirus (CMV) and BK virus will be listed by patient, and visit/time and if normal ranges are available, abnormalities will be flagged. The frequency of EBV, CMV and BK virus will also be summarized by treatment.

Adverse events

All information obtained on adverse events will be displayed by treatment and patient.

AEs and infections collected are to be coded with the MedDRA dictionary that gives preferred term and primary system organ class information. AEs and infection preferred terms are to be analyzed as a whole under the heading of AEs. Depending on the number of AEs in Part 2, the incidence of AEs will be summarized by body system, severity and relationship to study drug by the following where possible:

- AEs by primary SOC and PT
- AEs rated to have relationship to study drug by SOC and PT
- AEs by primary SOC, PT, and maximum severity
- SAEs by SOC and PT
- SAEs rated to have relationship to study drug by SOC and PT
- Deaths by SOC and PT

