7.1.3 Graphical presentation

Boxplots to visualize trends in longitudinal safety data (vitals, ECG, lab parameter) will be created.

A figure to represent the desirability of outcome ranking will be created.

Corporate Confidential Information

9 Reference list

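### The readable Part 2 SAP does not carry over the protocol's clinically notable laboratory flags, shift tables and change-from-randomization summaries, and its one selective laboratory listing would select almost nobody out

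*SAP*

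**What the plan says.** Protocol 9.5.3.2 treats laboratory data in two places.

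- Under Clinical laboratory evaluations: "All laboratory data will be listed by treatment, subject, and visit/time and if normal ranges are available, abnormalities will be flagged", with summary statistics by treatment and visit.
- Under Laboratory data, a second layer. It opens with the rule "Abnormalities according to clinically notable criteria will be identified". For the patient-level listing it says "Values outside of the clinically notable limits will be flagged". It then asks for tables of movement between categories: "Shift tables describing changes from randomization/enrollment based on the clinical notable criteria will be presented". It closes with summaries of the measured values, "including change from randomization/enrollment, will be generated by visit". Protocol 6.6.4 points to Appendix 7 for the limits.

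The Part 2 SAP has one general laboratory paragraph, in 7.1.2. Its first sentence, "All laboratory data will be listed by treatment, patient, and visit/time and if normal ranges are available abnormalities will be flagged", matches the protocol's first layer almost word for word. It then adds: "A separate listing is provided presenting all parameters in a patient with any abnormal values". Summary statistics by treatment and visit follow. SAP 7.1.3 adds: "Boxplots to visualize trends in longitudinal safety data (vitals, ECG, lab parameter) will be created".

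The readable SAP mentions neither clinically notable limits, nor shift tables, nor laboratory change from baseline. It does not say that they were withdrawn.

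**The concern.** Safety and tolerability against control is a secondary objective (SAP 1.3.2), assessed at Month 3 and again at Month 12. The combination under test is immunosuppressive, and Appendix 7 fixes in advance which laboratory values count as important. Examples are leukocytes at or below 2.0 k/mm³, granulocytes at or below 1,000/mm³, platelets below 50 k/mm³, and transaminases or bilirubin at 3 times the upper limit of normal or more. For creatinine after Week 4, the limit is 3 mg/dL or a rise of more than 30% over the preceding visit.

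If the SAP is followed as it reads, these limits are never applied in an output. The only selection rule left is a value outside the normal range, in people who have just received a kidney transplant and take mycophenolate and steroids. A rule that nearly everyone meets does not pick out the few patients whose values matter. The trial is also open-label. A rule fixed in advance treats both arms alike, whereas an adverse event report depends partly on the judgement of an investigator who knows the treatment.

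**Working it through.** **1. Protocol and SAP side by side**

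| Output in protocol 9.5.3.2 | Readable SAP 7.1.2–7.1.3 |
|---|---|
| Listing with normal-range flags | Present |
| Summary statistics by treatment and visit | Present |
| Appendix 7 values identified and flagged | Absent |
| Shift tables on Appendix 7 criteria | Absent |
| Change from randomization by visit | Absent |
| – | Added: listing of all parameters for patients with any abnormal value |
| – | Added: laboratory boxplots |

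**2. Whom would the any-abnormal listing select?**

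The documents give no rate of out-of-range values, so this is an illustration. Let f be the chance that one value is flagged (assumed) and m the number of values per patient, treated as independent (assumed; related analytes such as AST and ALT are not). The chance of at least one flag is 1 − (1 − f)^m.

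Inputs:
- Analytes: 9 hematology (protocol 6.6.4.1) + 25 chemistry (6.6.4.2) = 34.
- Local-laboratory draws in the Part 2 blood log (Appendix 1): 380 mL / 19 mL = 20.
- Of the 20, the four draws from 6 h to 72 h carry only five chemistry analytes, and screening, baseline and Day 1 may collapse into one. Counting only Day 15 and later leaves 20 − 4 − 3 = 13 full panels. Four of these fall by Day 85.

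| Panels counted | m | f = 1% | f = 5% |
|---|---|---|---|
| 1 | 34 | 28.9% | 82.5% |
| 2 | 68 | 49.5% | 96.9% |
| 4 (Days 15–85) | 136 | 74.5% | 99.9% |
| 13 (Days 15–337) | 442 | 98.8% | >99.9% |
| 20 (upper bound) | 680 | 99.9% | >99.9% |

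The 5% column corresponds to a healthy person judged against 95% reference ranges, so a higher rate in transplant recipients is the natural expectation. Over the full schedule the listing would hold nearly every patient even at 1%.

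This does not extend to each analyte. For one analyte over 20 draws, 1 − (1 − f)^20 is 18% at f = 1%, 40% at 2.5%, 64% at 5% and 99% at 20%.

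**3. Do the other outputs fill the gap?**

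- Visit summaries and boxplots work one visit at a time. Suppose 6 of 30 patients (20%) each crossed a limit once, at six different visits. Each visit would show one extreme value (1/30 = 3.3% of the arm), and no table would show the 20%.
- Individual profile plots are planned for platelets, coagulation and eGFR. The readable text plans none for white cells, neutrophils, transaminases or bilirubin.
- The eGFR model covers renal function only and excludes data after a treatment switch.
- The desirability ranking compares the most recent creatinine with its nadir (25% above). A transient rise of more than 30% between visits, which Appendix 7 would catch, can be missed.
- Adverse event tables include a laboratory value only if it causes signs or symptoms, is judged clinically significant or needs therapy (protocol 7.1).

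**4. What could the restored tables show?**

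With 15 control and 30 CFZ533 patients, a two-sided 5% test and assumed true rates of a notable value:

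| Control | CFZ533 | Power |
|---|---|---|
| 5% | 20% | 22% |
| 10% | 30% | 29% |
| 5% | 40% | 75% |

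Only a very large difference would be likely to reach significance. The tables would describe and raise signals, not test.

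**The case against.** **The arms can be compared without these tables.** A reader might infer that the arms cannot be told apart on laboratory safety. The documents do not support that. Flags mark listings; the comparison rests on summaries by treatment and visit, boxplots, the eGFR mixed model with a treatment difference and 90% confidence interval, the creatinine-based ranking and the adverse event tables. For a single analyte at one visit, 15 against 30 patients give 35%, 66% and 89% power for mean differences of 0.5, 0.75 and 1.0 SD. This objection stands. The loss is confined to categorical and shift information.

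**The normal-range flag is not a SAP invention.** A reader might infer that the SAP replaced the notable limits with normal ranges. It did not: the protocol has the same sentence. The gap is the missing second layer.

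**Nearly everyone is an assumption.** True: no rate is given, and the figures assume independence. They support the statement for the listing triggered by any abnormal value, not for each analyte, and they say nothing about comparing the arms.

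**Absence is not fully proven.** Parts of the SAP are blacked out. It refers to RAP documents in the plural, and others were not supplied. It was written from protocol v02 of 11 April 2016 and describes three parts, where the supplied protocol has two. The omission is therefore shown only for the readable text. But the laboratory paragraph itself is readable, and SAP 1.1 says that the SAP implements the protocol's analysis, so silence still leaves the two documents to be reconciled.

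**Important cytopenias surface elsewhere.** Partly. Thrombocytopenia and creatinine rise have patient-level output, and dose changes caused by adverse events are tabulated. For white cells, neutrophils and liver tests the route runs through the investigator's judgement.

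**Conclusion.** The point holds as a gap between protocol and SAP in safety reporting. Three laboratory outputs that the protocol requires are absent from the readable Part 2 SAP without explanation, and the SAP's own selective listing would include nearly every patient. As a result there is no rule-based view, by arm, of patients crossing clinically notable limits, most clearly for white cells, neutrophils and liver tests.

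The size is modest. The primary analysis, sample size and data collection are untouched, and averages by arm remain available. The conclusion about omission rests on the readable text and the supplied protocol version. The conclusion about the listing rests on assumed flag rates of 1% to 5% and independence.

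**What to change.** In SAP 7.1.2, under Clinical laboratory evaluations:

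1. Flag values against the Appendix 7 limits in the listings, beside the normal-range flags.
2. Restore the shift tables from randomization on those criteria, by arm. Use low, within and high categories where Appendix 7 gives two limits. Its creatinine limit applies only after Week 4, so the SAP should say how creatinine is shown, since a shift from randomization is not defined for it.
3. Restore change from randomization by visit and arm.
4. Trigger the separate listing on an Appendix 7 value instead of any value outside the normal range.

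Optionally, add the number of patients per arm with at least one post-transplant notable value, by parameter. The protocol does not ask for this count, but it is the shortest summary of the missing information. If any of items 1 to 3 was left out on purpose or is specified in another document, the SAP should say so.

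The cost is SAP wording and a few standard tables, with slightly more programming and no new data. With 30 against 15 patients, the tables should be labelled descriptive.
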